13.3 Sample Size and Accrual

Arm A: It's estimated that 23 subjects of confirmed PR or CR responses after initial nivolumab monotherapy will be enrolled (about 29% of total 80 subjects, accounting for 4% lost to follow-up from the overall enrollment of N=83). There is no prior data for this treatment strategy and the main purpose is to generate hypothesis and the assumptions were considered to be clinically meaningful from investigators perspectives. We assume that 1-year remission (continued CR/PR) rate of 10% is not acceptable and a true PR or CR rate of 35% or higher will be considered acceptable for the treatment strategy of nivolumab discontinuation. A single-arm design is employed with 23 eligible subjects entered. If 5 or more of the 23 subjects continue CR or PR at 1 year off nivolumab (observed rate of 22%), we will conclude that the treatment strategy warrants further study. The probability of concluding that the treatment strategy

effective is 7% if the true PR or CR rate is 10% and is >94% if the true PR or CR rate is 35% or higher.

Arm B: Approximately 57 subjects with PD or confirmed SD after initial nivolumab monotherapy will be available for the analysis. From historical data, the rates of PR/CR are 25%, SD 40%, PD 35% in patients treated with nivolumab. We assume that a PR/CR rate of 20% would be considered promising in this population who do not respond to nivolumab alone. The study uses Simon’s optimal two-stage design (Simon Controlled Clinical Trials 1989) to allow for early termination if evidence suggests that the addition of ipilimumab is inactive. 20 subjects will be enrolled in the first stage. If 1 or fewer PR/CR are observed, the enrollment of ipilimumab addition will be stopped. If 2 or more PR/CR are observed, then an additional 37 subjects will be enrolled for a total of 57 evaluable patients. The regimen will be declared worthy of further study if 6 or more PR/CR are observed. These decision rules result in 73% probability of stopping early (at the end of first stage) if the regimen is inactive. The design yields a 92% probability (statistical power) of declaring the regimen active given a true PR/CR rate of 20% or 4.7% probability (targeted type I error rate of 0.05) of declaring the regimen active given a true PR/CR rate of 5% or less.

A total accrual goal is 83 subjects. Subjects will continue study therapies till disease progressions, withdraw or adverse events. Additional 2-year follow-up after the end of treatments (EOT) is planned. The primary study analysis is expected to be at 2 years; 6 months for accrual, and 18 months from enrollment for last subject.

Accrual Targets				
Ethnic Category	Sex/Gender			
	Females		Males	Total
Hispanic or Latino	2	+	2	= 4
Not Hispanic or Latino	24	+	55	= 79
Ethnic Category: Total of all subjects	26	+	57	= 83
Racial Category				
American Indian or Alaskan Native	2	+	3	= 5
Asian	2	+	5	= 7
Black or African American	2	+	6	= 8

Native Hawaiian or other Pacific Islander	0	+	0	=	0
White	20	+	39	=	59
Racial Category: Total of all subjects	26	+	53	=	83

13.4 Analysis Datasets

Population	Definition
Enrolled	All subjects who meet the eligibility criteria and are registered onto the study.
Evaluable/Analysis	All subjects who receive at least one dose of trial drug or die before any evaluation.
Safety	All subjects with at least one dose of nivolumab or ipilimumab contribute data to the safety analysis.
Population	Definition
Treated	This will comprise all subjects who have been exposed to the planned course of treatment to any extent.

13.5 Assessment of Safety

Adverse event reports are to be submitted within 28 days of each clinic visit. All relevant adverse events will be reviewed by the DSMC for up to 4 times each year or more frequently if requested by the DSMC.

Arm A: As part of the early safety monitoring to make sure that discontinuation of nivolumab is not detrimental for subjects with initial confirmed PR/CR, futility assessments will be implemented after 9 (~39%) of the 23 subjects have image assessment (8 +/- 7 days) since discontinuing nivolumab: an estimate of PD rate with a two-sided binomial CI will be constructed. If 5 or more of the first 9 subjects experience PD (i.e, to have a lower bound of the CI $\geq 25\%$), then the enrollment of arm A may be suspended. The following table gives the operating characteristics of the early futility stopping; if the true unknown probability of PD rate is 60% or higher, the probability of observing 5 or more subjects with PD will be greater than 48% at the time of the first subsequent image assessment after discontinuing nivolumab.

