13.6 Operating Characteristics of Early Futility Stopping

True-unknown PD rate (%)	Probability of observing 5 or more PD among 9 subjects
30	0.03
40	0.1
50	0.25
60	0.48
70	0.73

For subjects who re-start nivolumab due disease progression, given there is no prior data for this treatment strategy, and the expected number of subjects to re-start nivolumab maybe small, the study team will monitor the non-response rate carefully. Similar futility analysis may take place at the subsequent image assessment to assess the risk of subjects no longer respond to nivolumab and decide if the strategy is not safe for subjects. The exact criteria will be determined as deemed clinically relevant.

Arm B: The safety review will be concurrent with the first efficacy review of PR/CR that is specified by the Simon two-stage design. Review of these safety data will be conducted by the study team and an independent DFCI Data and Safety Monitoring Committee (DSMC). Based on the review, the DSMC may advise that the study regimen be suspended for additional review. After this initial safety assessment, toxicity and adverse event data will be evaluated as part of the recurrent trial review by the DSMC.

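### The Arm A interim table in Section 13.6 gives the chance of 6 or more progressions among 9, although the stated trigger is 5 or more, so it understates the chance of reaching the trigger by 7 to 25 percentage points

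*Combined protocol and SAP*

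**What the plan says.** Section 13.5 plans an early check in Arm A once 9 of the 23 subjects have had imaging after stopping nivolumab. At that point "an estimate of PD rate with a two-sided binomial CI will be constructed". The trigger follows: "If 5 or more of the first 9 subjects experience PD (i.e, to have a lower bound of the CI" is at least 25%), "then the enrollment of arm A may be suspended". The same section then describes performance at a true PD rate of 60% or higher: "the probability of observing 5 or more subjects with PD will be greater than 48" per cent.

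Section 13.6 tabulates the rule under the column heading "Probability of observing 5 or more PD among 9 subjects". It prints 0.03, 0.1, 0.25, 0.48 and 0.73 for true PD rates of 30, 40, 50, 60 and 70%.

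The count is therefore given three times, twice in Section 13.5 and once in the table heading, and each time it is 5 or more. Section 13.5 does not give the level or the method of the interval that the 25% clause refers to.

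**The concern.** The 50% row can be checked without software. With 9 subjects and a PD rate of one half, the distribution is symmetric about 4.5, so the chance of 5 or more is exactly 0.50. The table prints 0.25. If one row is that far out, the column may have been computed for a different count.

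This matters because it is the only numeric group-level interim rule for Arm A. For the similar check in subjects who re-start nivolumab, Section 13.6 says only: "The exact criteria will be determined as deemed clinically relevant". The 5-of-23 rule in Section 13.3 applies at the end. Anyone who uses the table to judge whether the early check is sensitive enough, or too easily triggered, would be reading figures for another rule.

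**Working it through.** **Inputs.** n = 9 and a trigger of 5 or more (Sections 13.5 and 13.6); true PD rates p of 30% to 70% and the printed probabilities (Section 13.6); a lower confidence bound of at least 25% (Section 13.5). The exact two-sided 90% interval comes from Section 13.7.1, where it is specified for the Arm A one-year proportion. Applying it to the interim PD rate is an assumption.

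**Step 1: the printed column.** The upper tail is P(X ≥ r) = Σ C(9,k) p^k (1−p)^(9−k), summed over k = r to 9. At p = 0.5:

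- r = 6: (84 + 36 + 9 + 1)/512 = 130/512 = 0.2539, printed as 0.25.
- r = 5: (126 + 84 + 36 + 9 + 1)/512 = 256/512 = 0.5000.

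All rows:

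| True PD rate | Printed | P(X ≥ 6) | P(X ≥ 5) | P(X ≥ 5) minus printed, points |
|---|---|---|---|---|
| 30% | 0.03 | 0.0253 | 0.0988 | 6.9 |
| 40% | 0.1 | 0.0994 | 0.2666 | 16.7 |
| 50% | 0.25 | 0.2539 | 0.5000 | 25.0 |
| 60% | 0.48 | 0.4826 | 0.7334 | 25.3 |
| 70% | 0.73 | 0.7297 | 0.9012 | 17.1 |

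The 6-or-more tail reproduces every printed value to its rounding, and the 5-or-more tail reproduces none. Taking n = 8 or n = 10, with any cutoff from 4 to 7, does not give the printed column either. The pattern is what results from computing P(X > 5) where P(X ≥ 5) was meant.

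**Step 2: the same gap as a shift in PD rate.** Solving P(X ≥ 5) = printed value gives PD rates of about 22, 30, 39, 49 and 60%. The rows are labelled 30, 40, 50, 60 and 70%, so each is displaced by about 8 to 11 points.

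**Step 3: does the 25% clause fit a count of 5?** The exact lower bound L for x of 9 solves P(X ≥ x | L) = α/2.

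| Count | Exact 90% lower bound | Exact 95% lower bound |
|---|---|---|
| 4 of 9 | 16.9% | 13.7% |
| 5 of 9 | 25.1% | 21.2% |
| 6 of 9 | 34.5% | 29.9% |

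With the exact 90% interval, 5 is the smallest count that meets the clause. With an exact 95% interval it would be 6.

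**Step 4: how the plan computes its other Arm A count rule.** Section 13.3 reads: "If 5 or more of the 23 subjects continue CR or PR at 1 year off nivolumab", the strategy warrants further study. It states that the probability of declaring the strategy "effective is 7% if the true PR or CR rate is 10% and is >94" per cent at a rate of 35% or higher. With n = 23, P(X ≥ 5) = 0.0731 at 10% and 0.9449 at 35%, which matches. A 6-or-more count would give 2.3% and 86.9%, which does not. That rule was computed inclusively, as worded.

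**The case against.** The arithmetic mismatch cannot be defended, but which side of it is wrong can be argued. Because Section 13.5 gives no confidence level, one can suppose an exact 95% interval. The first count to reach 25% is then 6 of 9, which is the count the table uses, and the slip would lie in the wording. The support for 5 under the exact 90% interval is also narrow (25.1% against 25%), and Section 13.7.1 specifies that interval for the one-year response, not for the interim PD rate.

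This reading is coherent but less well supported. The count of 5 is stated three times and 6 nowhere. The 90% level is the one the plan uses for Arm A. A Wilson 95% interval also puts 5 of 9 above the bound, at 26.7%. What stands is that the interval must be named before the 25% clause can be checked.

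Two further points stand. The 48% statement is literally true of 5 or more, since 73% exceeds 48%; it is uninformative, not false. And the practical weight is modest: those running the trial would act on the count, not the table, and the outcome is a discretionary suspension of enrollment. If 5 is applied, a high PD rate is more likely to be flagged than the table suggests. The other side of this is more frequent triggering at low rates: 10% instead of 3% at a true PD rate of 30%.

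**Conclusion.** The concern holds. The Section 13.6 table does not describe the rule that Section 13.5 and its own heading state; it describes a 6-or-more rule. For the stated rule it understates the chance of reaching the trigger by 7 to 25 percentage points. At true PD rates of 40% to 50% it shows 10% to 25%, where the rule gives 27% to 50%.

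The mismatch between heading and column is a matter of exact binomial arithmetic and needs no assumption. Placing the slip in the table and the 48% sentence rests on the three consistent statements of the count, on the fit of the 25% clause under an exact 90% interval, and on the correct inclusive calculation in Section 13.3. These are probabilities of reaching a non-binding trigger, not of stopping. Nothing in the Section 13.3 sample size or error rates is affected. It should be fixed.

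**What to change.** - In Section 13.6, replace the column with the values for 5 or more of 9: 0.10, 0.27, 0.50, 0.73 and 0.90.
- In Section 13.5, replace the 48% statement with at least 73% at a true PD rate of 60% or higher.
- In Section 13.5, state the level and method of the two-sided interval. The exact 90% interval of Section 13.7.1 is consistent with the 25% clause at 5 of 9.
- If the sponsor intended an interval under which 5 of 9 falls short of 25%, such as an exact 95% interval, reconcile the count, the 25% clause and the table.

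The cost is a correction to one table and some wording. If the stated count stands, neither the sample size nor the conduct of the trial changes.

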13.6 Operating Characteristics of Early Futility Stopping

True-unknown PD rate (%)	Probability of observing 5 or more PD among 9 subjects
30	0.03
40	0.1
50	0.25
60	0.48
70	0.73

For subjects who re-start nivolumab due disease progression, given there is no prior data for this treatment strategy, and the expected number of subjects to re-start nivolumab maybe small, the study team will monitor the non-response rate carefully. Similar futility analysis may take place at the subsequent image assessment to assess the risk of subjects no longer respond to nivolumab and decide if the strategy is not safe for subjects. The exact criteria will be determined as deemed clinically relevant.

Arm B: The safety review will be concurrent with the first efficacy review of PR/CR that is specified by the Simon two-stage design. Review of these safety data will be conducted by the study team and an independent DFCI Data and Safety Monitoring Committee (DSMC). Based on the review, the DSMC may advise that the study regimen be suspended for additional review. After this initial safety assessment, toxicity and adverse event data will be evaluated as part of the recurrent trial review by the DSMC.

13.7 Efficacy Analysis

13.7.1 Primary Efficacy Analysis

Tumor assessment will be performed every 8 weeks. At the time of each restaging, subjects will be classified as achieving complete response (CR), partial response (PR), stable disease (SD), progressive disease (PD), or non-evaluable for response according to RECIST (Version 1.1) criteria.

Arm A: The proportion of subjects with sustained/continued PR or CR during the 1 year since the nivolumab discontinuation will be presented with a two-sided 90% CI using exact binominal method. Based on a sample size of 23 subjects, the confidence interval will be no wider than 0.37. For a targeted 35% PR or CR rate, the estimated PR or CR rate precision (width of two sided 90%CI) would be 0.35.

Arm B: The proportion of subjects with PR or CR during the 1-year from the date of first dose of ipilimumab will be presented with a two-sided 90% confidence interval calculated using the method of Atkinson and Brown, corresponding to the two-stage design.

13.7.2 Secondary Analysis

PFS and OS: The progression-free survival (PFS), and overall survival (OS) will each be summarized using the product-limit method of Kaplan-Meier. Median times for each endpoint will be presented with two-sided 90% confidence intervals estimated using log(-log(survival)) methodology. Kaplan-Meier estimates of PFS at 6 or 12 months may also be presented with two-sided 90% confidence intervals.

Salvage Therapy-Free Interval: The proportion of subjects re-start nivolumab since nivolumab discontinuation (arm A) during 1-year will be estimated with two-sided 90% confidence intervals. In addition, the reasons for re-starting nivolumab (Arm A) will be tabulated.

Subset analysis of study endpoints will be explored according to IMDC* risk group (favorable, intermediate, versus poor risk); prior systemic treatment for RCC (yes versus no); first line versus second line targeted therapy; histology (clear cell versus non-clear cell RCC subtypes; sarcomatoid components present versus absent)

*IMDC risk factors include ECOG < 1, time from original diagnosis to treatment less than one year, hemoglobin less than the lower limit of normal, and serum calcium, neutrophil count, or platelet count greater than the upper limit of normal

Immune Related Objective Response Rate: The proportion of subjects with immune ORR will be presented with two-sided 90% confidence interval estimated using exact binomial methods.

Safety and Tolerability: All adverse events recorded during the trial will be summarized for the safety population. The incidence of events that are new or worsening from the time of first dose of treatment will be summarized according to system organ class and/or preferred term, severity (based on CTCAE version 4), type of adverse event, and relation to study treatment.

The worst grade will be used if any toxicity event is reported multiple times on the same participant. All adverse events resulting in discontinuation, and/or dosing interruption, and/or treatment delay will also be summarized.

Given the potential multiple treatment sequences, the incidence of events (grade 3+) will be summarized according to treatment arms as well as the type of therapies they are on at the time of events.

Deaths reportable as SAEs and non-fatal serious adverse events will be listed by patient and tabulated by primary system organ class, and type of adverse event.

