- Subjects who experience stable disease (SD) at the initial response assessment at 8 weeks from initiation of primary nivolumab therapy, with the subsequent scan in 8 weeks (± 7 days) documenting CR/PR which is maintained at the next imaging assessment in 8 weeks (± 7 days) (i.e., ~24 weeks from initiation of nivolumab).

Patients who have SD on initial assessment followed by CR/PR on first confirmatory assessment which does not persist on the second confirmatory imaging assessment will be allocated to Arm B as CR/PR was not persistent and confirmed on consecutive imaging assessments.

Subjects with confirmed PR/CR (arm A) will discontinue nivolumab and be followed with serial imaging assessments every 8 weeks. If progressive disease (PD) develops, therapy with nivolumab will be resumed and will not be discontinued if a subsequent PR or CR were to occur. Subjects who experience subsequent PD following re-initiation of nivolumab, will be treated with nivolumab + ipilimumab every 3 weeks x 2 doses and will continue nivolumab. All patients will continue on treatment with nivolumab alone every 4 weeks which will begin 5 weeks \pm 3 days after the last dose of nivolumab + ipilimumab. For subjects who experience a PD on nivolumab and ipilimumab, treatment will be discontinued.

If by 24 weeks, subjects have not demonstrated a persistent CR/PR confirmed on at least two serial scan assessments, then subjects will be allocated to Arm B at the 24 week time point.

Arm B (persistent PD/SD) includes the following patient scenarios:

- Subjects who experience PD at 8 weeks (initial response assessment) on primary nivolumab therapy which is then confirmed by a second scan within 4 weeks (\pm 7 days). The confirmatory scan is not required if the site investigator determines that this is clinically detrimental;
- Subjects who initially experience SD at 8 weeks (initial response assessment), which is confirmed with a second scan showing SD in 8 weeks (\pm 7 days)
- Subjects who have received at least 3 doses of nivolumab and may have signs and/or symptoms concerning for early clinical progression with radiographic evidence of PD before 8 weeks
- Subjects who do not meet the criteria for allocation into Arm A given lack of persistent CR/PR confirmation on serial and consecutive imaging within the first 6 months of the study will be allocated to Arm B by the 6-month time point.

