6. TREATMENT PLAN

After informed consent has been obtained in writing, the subject will then undergo screening procedures and will enter the trial after successful screening. The subject must be willing to undergo a MANDATORY fresh tumor biopsy prior to treatment following successful screening and registration unless the site investigator deems the procedure medically unsafe.

Subjects who have signs and/or symptoms concerning for early clinical progression can undergo imaging before the initial 8 week imaging time point. In this scenario, if there is evidence of radiographic progression as per RECIST version 1.1, subjects will be allocated immediately to Arm B as long as they have received at least 2 doses of nivolumab (two doses of 480mg IV q 4 wks). Subjects who received fewer than 2 doses of nivolumab (480mg dosing) with early progression can either discontinue from study or may continue on to receive at least 2 doses of nivolumab before reassessing response at treating investigator's discretion. The per protocol 8 week scans should still be done on schedule even if earlier scans are done and compared to baseline for initial response assessment which should then be confirmed at the 16 week time point per protocol.

Primary Treatment with Nivolumab

Eligible subjects will be enrolled and will receive primary treatment with nivolumab 480 mg IV (D1) for 2 cycles. Each Cycle = 28 days. After 2 cycles (8 weeks +/- 7 days), all subjects will have initial disease assessment scans.

Arm A: CR or PR Response after Primary Treatment with Nivolumab:

- For subjects allocated to Arm A, nivolumab will be discontinued and subjects will be followed with serial imaging assessments every 8 weeks (Observation).
- If PD develops, therapy with nivolumab 480 mg IV every 4 weeks will be resumed. At this time, subjects will be asked to undergo an optional fresh tumor biopsy. Subjects will have disease assessment scans every 8 weeks (+/- 7 days). Nivolumab will continue until PD is documented.

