DISEASE ASSESSMENT									
CT of chest ³							X ³		
CT or MRI of abdomen and pelvis ³							X ³		
TREATMENT EXPOSURE									
Nivolumab		X	X	X		X			
Ipilimumab			X	X					
SPECIMEN COLLECTION									
Tumor Biopsy ¹⁰	X	X						X	
Research Blood Sample- Biomarkers ¹¹	X	X					X	X	
Research Blood Sample- cfDNA and CTCs ¹²	X	X					X	X	
FOLLOW-UP									
Survival Status, Subsequent Therapy									X

Key to Footnotes:

- 1: Vital signs to include upright blood pressure, heart rate, respiratory rate, temperature, oxygen saturation, body weight (kg) and height (cm). Height at SCREENING ONLY.
- 2: Hematology testing to include full CBC with WBC, ANC, hemoglobin, and platelet count and differential. Serum chemistry to include full comprehensive metabolic panel with sodium, potassium, chloride, bicarbonate, BUN, creatinine, glucose, calcium, albumin, AST, ALT, alkaline phosphatase, and total bilirubin. CID1 laboratory assessments do not need to re-meet eligibility criteria. TSH and free T4 will be done every two cycles (8 weeks \pm 7 days), except when ipilimumab is added, TSH and free T4 will be obtained after 3 cycles (12 weeks \pm 7 days) instead of 2 cycles (8 weeks) to align with scans.
- 3: Diagnostic CT chest and CT or MRI of the abdomen and pelvis should be obtained every 2 cycles (\pm 7 days). **NOTE:** When ipilimumab is added, the first set of post-ipilimumab imaging will be obtained after 3 cycles (~12 weeks \pm 7 days) instead of 2 cycles. After the initial set of scans after ipilimumab initiation, the scan timing will revert back to every 2 cycles (\pm 7 days). If dosing is delayed, imaging should follow guidelines of cycles over absolute weeks.
- 4: **OBSERVATION:** Subjects with a CR/PR (Arm A) after Primary Treatment with nivolumab will have nivolumab discontinued and go onto Observation. Radiology imaging will be done every 2 cycles (8 weeks \pm 7 days) as described in bullet 3. Subjects will continue observation until PD. During the observation period subjects will be seen in clinic once per cycles (28 days \pm 3 days). For subjects who have shown persistent CR/PR while on observation, in clinic study visits can be extended to every 8 weeks. A nurse, NP/PA, or physician will call subjects in between visits for assessment of symptoms (at least every 4 weeks). This must be approved by sponsor-investigator prior to modifying subjects visit schedule.

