- 5: **RE-INITIATION OF NIVOLUMAB:** Subjects that experience PD during observation will re-initiate nivolumab. Radiology imaging will be done every 2 cycles (8 weeks \pm 7 days) as described in bullet 3. Subjects will continue nivolumab until PD.
- 6: **ADDITION OF IPILIMUMAB:** Subjects that show PD after re-initiation of nivolumab will have ipilimumab added for 2 doses ONLY. During this time, nivolumab will be given every 3 weeks to match ipilimumab administration. Disease assessment scans will occur after completion of 3 cycles (12 weeks \pm 7 days) from the time ipilimumab is added to nivolumab. Nivolumab ALONE will be continued starting 5 weeks \pm 3 days after last dose of nivolumab PLUS ipilimumab at the start of cycle 3/day 1 from when ipilimumab is added to nivolumab.
- 7: **CONTINUATION OF NIVOLUMAB:** Subjects with CR/PR/SD after initial scans following the addition of ipilimumab to nivolumab will continue nivolumab ALONE until PD. During this time nivolumab will be given every 4 weeks and disease assessment scans will occur every 2 cycles (8 weeks \pm 7 days). Subjects will be permitted to continue treatment beyond site investigator assessed progression as long as they meet the following criteria: (1) Site investigator-assessed clinical benefit AND (2) Subject is tolerating study drug.
- 8: End of treatment (EOT) visit will occur 30 days (\pm 7 days) after last dose of study drug. Subjects will come off study treatment if they have PD as described in bullet #6 or for other reasons such as toxicity or subject choice. Subjects who (1) had study drugs delayed or modified due to toxicity or other factors and (2) were then discontinued from study treatment can use a study visit as EOT visit. Subjects who have an ongoing study treatment-related AE upon discontinuation from the study treatment will be followed until the event has resolved to baseline grade, the event is assessed by the site investigator as stable, new anticancer treatment is initiated, the subject is lost to follow-up, the subject withdraws consent, or until it has been determined that study treatment or participation is not the cause of the AE. If not seen in clinic, subjects will be called on day 100 following the last dose of study drug for assessment of adverse events.

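### Grade 3+ incidence by therapy has no per-therapy denominator or time at risk, although the therapy periods differ several-fold in length, so the crude figures are not comparable across therapies

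*Combined protocol and SAP*

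**What the plan says.** Section 13.7.2, under safety and tolerability, notes that subjects may pass through several treatment sequences and then plans that "the incidence of events (grade 3+) will be summarized according to treatment arms as well as the type of therapies they are on" when the event occurs. The counting rule is: "The worst grade will be used if any toxicity event is reported multiple times on the same participant". Whether that rule starts again in each therapy period is not stated.

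The only safety denominator is in Section 13.4: "All subjects with at least one dose of nivolumab or ipilimumab contribute data to the safety analysis". It covers all treated subjects and is not specific to a therapy. No person-time, fixed window or exposure-adjusted rate is planned.

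The lengths of the periods come from elsewhere in the protocol:

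- **Primary nivolumab.** Section 6: "Eligible subjects will be enrolled and will receive primary treatment with nivolumab 480 mg IV (D1) for 2 cycles". Dosing then continues while response is confirmed. Under Section 2.7, if no persistent response has been confirmed by 24 weeks, "then subjects will be allocated to Arm B at the 24 week time point".
- **Combination.** Doses on Day 1 and Day 22. Section 8, Arm A calendar, footnote 6: "Nivolumab ALONE will be continued starting 5 weeks". The footnote allows a 3-day tolerance, counts the interval from the second combined dose, and places the restart at Cycle 3 Day 1. Arm B calendar footnote 4 says the same.
- **Observation, resumed nivolumab, nivolumab after the combination.** All run until progression (Arm A calendar footnotes 4, 5 and 7; Arm B calendar footnote 5).

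**The concern.** The sentence exists to separate the toxicity of different therapies within one sequence. A proportion with at least one grade 3+ event grows with the time watched, so two therapies with the same event rate give different proportions if one period is longer. A true difference in rate can also be hidden or reversed. Correct assignment of each event to a therapy does not cure this, because the events would still be counted over unequal time.

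Safety in Arms A and B is a secondary objective (Section 3.1.2), and this is the only by-therapy safety summary planned. Readers will compare its columns, and without an exposure summary they cannot correct for period length themselves.

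**Working it through.** The plan states no figure for this summary, so there is none to reproduce. The check uses the schedule and stated assumptions.

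**1. Period lengths (Sections 2.7, 6 and 8)**

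- Combination: Day 1 to Day 22 is 21 days; 5 weeks more is 35 days; 21 + 35 = 56 days = 8 weeks, so nivolumab alone restarts on Day 57.
- Primary nivolumab: 2 × 28 days = 8 weeks to the first scan, and up to 24 weeks before allocation.
- Observation, resumed nivolumab, continued nivolumab: no upper limit. One year is the Arm A endpoint window, not the length of a period.

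**2. Equal hazard, everyone followed for the whole period**

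Assumption: constant hazard h per month, the same in every period. Incidence = 1 − exp(−h × weeks/4.345).

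| h per month | 8 weeks | 16 weeks | 24 weeks | 52 weeks |
|---|---|---|---|---|
| 1% | 1.8% | 3.6% | 5.4% | 11.3% |
| 2% | 3.6% | 7.1% | 10.5% | 21.3% |
| 3% | 5.4% | 10.5% | 15.3% | 30.2% |

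At 2%, 24 weeks gives 10.5/3.6 = 2.9 times the 8-week figure with no true difference.

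**3. Observation with exit**

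The 52-week column overstates observation, which ends at progression. Section 13.3 uses one-year remission of 10% (unacceptable) and 35% (acceptable). Treating loss of remission as exit at a constant rate λ (an approximation), with 52/4.345 = 11.97 months:

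- 10%: λ = −ln(0.10)/11.97 = 0.192 per month
- 35%: λ = −ln(0.35)/11.97 = 0.088 per month

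Incidence while under observation = h/(h + λ) × [1 − exp(−(h + λ) × 11.97)]. With h = 0.02:

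- 10%: 0.02/0.212 × (1 − exp(−2.54)) = 8.7%
- 35%: 0.02/0.108 × (1 − exp(−1.29)) = 13.5%

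Against 3.6% for the 8-week block, that is about 2.4 to 3.7 times.

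**4. Unequal hazards**

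Section 2 gives grade 3–4 treatment-related events in 76/406 = 18.7% on nivolumab and 6/21 = 28.6% on nivolumab 3 mg/kg plus ipilimumab 1 mg/kg. It does not give the time over which they accrued, so assume 26 and 12 weeks.

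- Nivolumab: −ln(1 − 0.187)/26 = 0.80 per 100 patient-weeks
- Combination: −ln(1 − 0.286)/12 = 2.80 per 100 patient-weeks; ratio 3.5

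Crude incidence is then 20.1% for 8 weeks of combination, against 12.0%, 17.4% and 33.9% for 16, 24 and 52 weeks of nivolumab. A 3.5-fold rate difference shows as 20.1% against 17.4% at 24 weeks and reverses at 52. The ratio depends heavily on the assumed times: with 8 to 36.6 weeks for the combination and 20 to 52 for nivolumab it runs from 0.9 to 10.6.

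In general, 8 weeks of combination matches 16, 24 or 52 weeks of nivolumab when its rate is 16/8 = 2, 24/8 = 3 or 52/8 = 6.5 times as high.

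**The case against.** The best defence is that this is one descriptive, secondary summary with no planned test between therapies. Nothing forbids an exposure table later, and person-month rates have a cost of their own: they assume a roughly constant hazard within a period and will be imprecise. That limits the severity. It does not supply the missing denominator or make the columns comparable.

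Four stronger readings are tempting, and the documents do not support them.

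- **The table ranks therapies by exposure time.** It need not. In step 4 the 8-week combination ranks above 16 and 24 weeks of nivolumab. If the hazard off drug were 10% of the nivolumab hazard, 52 weeks of observation would give 4.1%, below the 6.2% for 8 weeks on nivolumab.
- **There is a six-fold spread.** The 52-week figure of 21.3% against 3.6% requires every Arm A subject to be observed for the full year, which the plan's own remission rates contradict.
- **Unequal visit frequency biases the comparison.** A reader may note that for observation "in clinic study visits can be extended to every 8 weeks". That applies only to persistent responders, needs sponsor-investigator approval, and comes with symptom calls at least every 4 weeks. Primary nivolumab has a Cycle 1 Day 15 visit, so its first 8 weeks have visits on Days 1, 15, 29 and 57, against Days 1, 22, 43 and 57 in the combination block: the same number. Denser visits would also raise the combination count while its short length lowers it.
- **The trial's safety case rests on this table.** Stopping nivolumab is also guarded by the progression rule in Sections 13.5 and 13.6, and adding ipilimumab by study-team and DSMC review (Sections 13.6 and 14.2). Section 13.7.2 plans other adverse-event summaries as well.

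**Conclusion.** The point holds in a limited form. As planned, by-therapy grade 3+ incidence has no per-therapy denominator and no time at risk, while the periods differ several-fold in length. The crude figures mix rate with exposure and cannot do the separating that the sentence intends.

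Under an identical assumed hazard of 2% per month, the artefact is roughly three-fold between 8 and 24 weeks, and 2.4- to 3.7-fold between the combination block and observation. The multiples change little at 1% or 3% per month. They rest on constant hazards and, for observation, on treating loss of remission as exit. The hazards themselves are assumptions, not values from the documents. The direction of any distortion in the real data cannot be predicted.

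The issue is worth correcting before the analysis. It does not touch the primary endpoints or the stopping rules.

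**What to change.** In Section 13.7.2:

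- Use as denominator for each therapy the subjects who entered that period: primary nivolumab, observation, resumed nivolumab, combination, and nivolumab after the combination.
- Apply the worst-grade rule within each period.
- Report n/N with total person-time, and first grade 3+ events per 100 person-months with exact Poisson 90% CIs. Time runs from the start of the period to the first event or the end of the period.
- Add cumulative incidence over the first 8 weeks of each therapy, the length of the combination block, and say how subjects who leave a period sooner are counted.

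The cost is SAP wording and one more table, from dosing and adverse-event dates already collected. No visit, treatment or sample size changes. The downside is wide intervals in small periods, which shows fairly how little those periods can say. The rate also averages over a hazard that may change within a period, so it should stand beside the 8-week figure and not replace it.
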